Study population: Treatment seeking cocaine dependent subjects (N=80), aged 18-65 years Design: After eligibility screening and informed consent, participants will undergo a baseline phase during which they will be randomized to receive high-frequency (15Hz) rTMS (active rTMS) or sham stimulation of the left DLPFC. Subsequently, the continued treatment phase will take place, during which rTMS sessions will be conducted twice per day, five times per week for 2 weeks, for a total of 20 sessions. During this phase, participants will also undergo self-help groups twice a week. After this phase, participants will start a 24-week outpatient phase. (2) During the first 12 weeks (rTMS follow-up) participants will undergo real or sham

stimulation (two consecutive sessions weekly), and behavioral assessments will be performed.

During the following 12 weeks (no rTMS follow-up), participants will not receive TMS but behavioral data will be collected to observe long-term effects of rTMS. Visits will take place every two weeks, during this phase. During the follow-up period, patients will continue to participate in self-help groups.

Outcomes measures: Our primary outcomes will be: (1) change in craving score as measured by the CCQ from pre- to post treatment [baseline and after rTMS treatment: 2 weeks, 3 months, 6 months]; (2) changes in cocaine consumption as measured by TLFB self-reports and urine drug screen from pre- to post treatment [baseline and after rTMS treatment: 2 weeks, 3 months, 6 months]. Our secondary outcomes are: Changes in the scores on the 90 Symptoms Questionnaire (SCL-90) from pre- to post treatment [baseline and after rTMS treatment: 2 weeks, 3 months, 6 months]; (2) changes in the scores of the Montgomery-Asberg Depression Scale (MADRS) from pre- to post treatment [baseline and after rTMS treatment: 2 weeks, 3 months, 6 months]; (3) changes in the scores on the Hamilton Anxiety Rating Scale (HARS); (4) changes in the scores on the frontal assessment battery (FAB), and on the Flanker task from pre- to post treatment [baseline and after rTMS treatment: 2 weeks, 3 months, 6 months];

(5) changes in the scores of the Iowa Gambling Task from pre- to post treatment [baseline and after rTMS treatment: 2 weeks, 3 months, 6 months];

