Subjects will be seated in a recliner with their hands in a comfortable resting position, and the study investigator will insert earplugs, while the participant will wear a cap over the scalp. After skin preparation, surface electrodes will be taped over the region of the abductor pollicis brevis (APB) belly and associated tendon of the right hand. The coil will be placed over the hand-associated primary motor cortex of the right hemisphere with the handle directed posteriorly. While supra-threshold stimuli will be applied, the coil will be moved in steps of 1 cm to determine the optimal scalp position for producing motor evoked potentials (MEP) of maximal amplitude (lowest threshold) in the contralateral target hand muscle. This procedure will be performed in order to identify the resting motor threshold (RMT), which will be used to calculate the intensity of stimulation (100% of the RMT). Subsequently, the coil will be placed over the left dorsolateral prefrontal cortex using a TMS Navigator. The motor hotspot and the DLPFC location will be marked on the cap wore by the participant so to ensure accuracy and consistency across sessions. Two consecutive rTMS sessions lasting 13 minutes each will be performed, with a minimum of 60 minutes interval between sessions. Each rTMS session will be delivered at the intensity of 100% of individual resting motor threshold, for a total of 40 trains (60 stimuli per train, inter-train interval of 15 seconds, for a total of 2400 stimuli). At the beginning of each session, participants will be exposed to cocaine-related cues for approx. 2 minutes. While viewing pictures (approx. 60 images), participants will be instructed to try to inhibit any craving elicited by the cues in an attempt to elicit activation in networks specifically related to controlling responses and cocaine use/substance abuse in general. At the end of each stimulation session, participants will rate their craving using a Visual Analogue Scale (VAS).

Study days during which participants will receive stimulation will be planned as follow:

Arrival
 Tox drug screen
 Preparation (earplugs, cap)
 RMT*
 TMS (active or placebo) and cocaine-cues exposure
 HR/PB monitoring
 VAS cocaine craving
 Side effects questionnaire and PANAS

9. Interval > 60 minuti

10. Steps 6,7 and 8 will be repeated

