Side effects: People are at risk for injury from the MRI magnet if they have pacemakers or other implanted electrical devices, brain stimulators, aneurysm clips (metal clips on the wall of a large artery), metallic prostheses (including metal pins and rods, heart valves, and cochlear implants), permanent eyeliner, implanted delivery pump, or shrapnel fragments. Welders and metal workers are also at risk for injury because of possible small metal fragments in the eye of which they may be unaware.

Risk Minimization: The patients are screened using the NMR center safety screening form prior to the study and will not receive an MRI scan if the screen is positive. Women who are pregnant may not undergo a research MRI. All women of childbearing potential will have a pregnancy test performed, which must be negative, before proceeding. Individuals with fear of confined spaces may become anxious during an MRI. There are no known long-term risks or consequences of MRI scans. The length of scan varies from 45 min to 120 min maximum

Questionnaires and Rating Scales

- Adult ADHD Self-Report Scale (ASRS): This questionnaire is an 18-item checklist designed by the World Health Organization (WHO) and Workgroup on Adult ADHD to determine whether a participant is suffering from symptoms related to attentiondeficit/hyperactivity disorder. Completion time: ~ 5 minutes.
- TMS Safety Screen: A questionnaire that aids in determining appropriateness of administering TBS. Completion time: < 5 minutes.

- Toronto Alexithymia Scale (TAS-20): A 20-item self-report questionnaire to assess emotional awareness. Completion time: ~ 10 minute.
- Cocaine Craving Questionnaire (CCQ): This measure includes 45 items that measure current craving for cocaine. Completion time: ~ 10 minutes.
- Sensation Seeking Scale V (SSS-V, 127): A 40-item self-report questionnaire that assesses individual differences in sensation seeking. Completion time: < 10 minutes.
- Cocaine Selective Severity Assessment (CSSA): to measure cocaine withdrawal signs and symptoms. Completion time minutes: ~ 5 minutes.

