As time permits during the screening visit and after consenting, baseline characterization measures will also be collected. Participants may be scheduled for an additional visit and the necessary additional time to complete these assessments prior to beginning the 10-day rTMS treatment session. Following this, subjetes will have 8 follow-up visits [at the end of continued rTMS treatment phase, at rTMS follow-up visit #2, #4, #8, #12, and once a month during no rTMS follow-up phase].

Characterization measures include:

- Hamilton Anxiety Scale (HARS): A 21-item self-report inventory, which assesses the severity of anxiety. Completion time: ~ 5 minutes.
- Montgomery-Asberg Depression Rating Scale (MADRS): A clinical assessment to identify symptoms of depression. This assessment is especially useful in identifying changes in depression symptoms over time. Completion time: < 10 minutes.
- Positive and Negative Affect Scale (PANAS): A self-report scale to assess state-level affect. Completion time: < 5 Minutes.
- Profile of Mood States (POMS): A questionnaire designed to measure present mood state by a list of adjectives on a 5-point Likert scale and measures six dimensions of affect, including tension-anxiety, depression-dejection, anger-hostility, vigor-activity, fatigue-inertia, and confusion-bewilderment. The measure has been shown to produce reliable and valid profiles of mood state. Completion time: ~ 5 minutes.
- Snaith-Hamilton Pleasure Scale (SHAPS): A 14-item self-report scale designed to measure hedonic-tone/anhedonia. Completion time: ~ 5 minutes.
- Temporal Experience of pleasure Scale (TEPS): A 20-item self-report scale designed to evaluate individual trait dispositions in anticipatory and consummatory pleasure experiences. Completion time: ~ 15 minutes.

- Quality of Life Enjoyment and Satisfaction Questionnaire Short Form (Q-LES-Q-SF): A self-report scale designed to measure social ties between the participants and their friend, family, co-workers, etc. Completion time: ~ 15 minutes.
- Time-line follow back (TLFB). The TLFB will be used to assess substance use behavior. This assessment will be either self-administered or administered by one of the investigators. Participants will read the instructions and/or will be guided by the therapist or investigator in filling out the calendar. A lifetime TLFB will be administered at baseline and during each visit.
- Columbia-Suicide Severity Rating Scale (C-SSRS):to assess suicidality ideation.

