 Completion time: < 5 min.
- Brief Psychiatric Rating Scale (BPRS- brief version): to assess psychiatric symptoms. Completion time: 15 min.
- Visual Analogical Scale for Food Craving (VAS food): to assess food craving.
 Completion time: ~ 5 min.
- Insomnia severity index (ISI): to evaluate sleep patterns and quality. Completion time:

 ∼ 3 min.
- Symptom Checklist-90-R (SCL-90-R): brief self-report psychometric instrument to evaluate a broad range of psychiatric symptoms and to measure the progress and outcome of psychiatric and psychological treatments. Completion time: ~ 15 min.

Executive and Cognitive Function will be assessed at baseline, at the end of continued rTMS treatment phase, at the end of rTMS follow-up phase and at the end of the no rTMS follow-up phase. Executive Function and Cognitive Assessment include:

- Frontal Assessment Battery (FAB): to assess frontal dysexecutive phenotype. Completion time: ~ 10 min.
- Eriksen Flanker Task (Flanker): to assess the ability to suppress responses that are inappropriate in a particular context. Completion time: ~ 15 min.
- Iowa Gambling Task: to assess decision-making process. Completion time: ~ 15 min.

E. Study Design

The study itself will consist of three phases.

- (1) an outpatient screening phase, during which patients will be screened to assess their eligibility to be enrolled in the study. This phase will include informed consent and randomization, and will conclude with baseline data collection.
- (2) a continued rTMS treatment phase, during which subjects will receive 20 stimulation sessions (2 daily, 5 days/week). In addition to this, participants will also attend self-help groups twice per week, as part of standard-of-treatment for CUDs.

During this phase, treatment response will be assessed by evaluating cocaine craving and consumption, psychiatric and medical symptoms and functioning.

(3) a follow-up phase of 24 weeks, which will be structured as following. During the first 12 weeks (rTMS follow-up) subjects will be asked to return to the Outpatient Clinic for an outpatient visit. During these visits, participants will undergo real or sham stimulation (two consecutive sessions per day), and will also attend self-help groups once per week.

During the following 12 weeks (no rTMS follow-up), participants will not receive TMS but behavioral and other data will be collected to observe long-term effects of rTMS.

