- Changes in CCQ score between the active rTMS and sham group, and from pre- to post treatment [baseline and after rTMS treatment: 2 weeks, 3 months, 6 months];
- Percent of negative urine samples between the active rTMS and sham group, and from pre- to post treatment [baseline and after rTMS treatment: 2 weeks, 3 months, 6 months].

Secondary aims:

- Changes in the scores on the 90 Symptoms Questionnaire (SCL-90) from pre- to post treatment [baseline and after rTMS treatment: 2 weeks, 3 months, 6 months];
- Changes in the scores of the Montgomery-Asberg Depression Scale (MADRS) from pre- to post treatment [baseline and after rTMS treatment: 2 weeks, 3 months, 6 months];
- Changes in the scores on the Hamilton Anxiety Rating Scale (HARS);

- Changes in the scores on the frontal assessment battery (FAB), and on the Flanker task from pre- to post treatment [baseline and after rTMS treatment: 2 weeks, 3 months, 6 months];
- Changes in the scores of the Iowa Gambling Task from pre- to post treatment [baseline and after rTMS treatment: 2 weeks, 3 months, 6 months];

Exploratory aims:

- DLPFC BOLD signal change in response to cocaine-related cues from baseline to each time point, and between the active and sham group;
- Changes in resting state functional connnectivity between the DLPFC and other nodes of the executive control network (ECN), from baseline to each time point, and between the active and sham group.

Statistical Analysis

Behavioral measures on each of the cognitive tasks as well as questionnaire data from each of the experimental conditions will be compared both within and between experimental groups using mixed, repeated-measures ANOVA, and linear mixed models. When assessing the statistical results from the behavioral and questionnaire data, a standard α -level of 0.05 will be used. Alpha-levels for multiple comparison follow-up tests will be corrected using an appropriate method (e.g., Bonferroni, Tukey, Scheffe).

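### Craving change is measured from one listed baseline CCQ reading; a second reading before the first stimulation, averaged and used as a covariate, would be a cheap but optional gain in precision

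*Combined protocol and SAP*

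**What the plan says.** The synopsis and section F (Objectives, Outcomes measures) define primary outcome 1 as "change in craving score as measured by the CCQ from pre- to post treatment [baseline and after rTMS treatment: 2 weeks", then 3 months and 6 months. The primary aim in section F adds the comparison between arms: "Changes in CCQ score between the active rTMS and sham group, and from pre- to post treatment". All three places list one time point before treatment, and none mentions a repeat or an average.

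Section D (Questionnaires and Rating Scales) says of the CCQ: "This measure includes 45 items that measure current craving for cocaine. Completion time: ~ 10 minutes".

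Three contacts before stimulation are described:
- **Screening phase (section E):** "This phase will include informed consent and randomization, and will conclude with baseline data collection".
- **An optional visit before treatment starts (section D):** "Participants may be scheduled for an additional visit and the necessary additional time to complete these assessments". It is tied to the baseline characterization measures, and the CCQ is not in that list.
- **The first stimulation day (section D, rTMS):** arrival, drug screen, preparation and motor threshold all come before the step "TMS (active or placebo) and cocaine-cues exposure". No CCQ is listed for that day. The VAS craving rating comes only after stimulation, so it cannot serve as a second baseline reading.

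The Statistical Analysis section names mixed repeated-measures ANOVA and linear mixed models. It does not say whether baseline is a covariate.

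**The concern.** A score for current craving at one visit mixes the participant's usual level with that day's fluctuation. If the outcome is change from that score, the same fluctuation is subtracted from the 2-week, 3-month and 6-month values. It widens the interval for the active-sham difference at each time point and makes the three craving results move together. The plan sizes the trial on 30 analysed participants per arm, and every treated participant already attends on the first stimulation day before any stimulation. A second reading could be taken then, but it cannot be recovered once stimulation has begun.

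**Working it through.** **Inputs from the Power Analysis paragraph (section F).** Cohen's d = 0.65, one-tailed alpha 0.05, about 30 per group analysed, 40 per group recruited, retention 80-85%. Power is not stated, nor is the SD on which d is standardised.

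**The plan's own figure.** A two-sample t-test with d = 0.65 and one-tailed 0.05 needs 29.97 per group for 80% power, so the stated 30 is reproduced. At 30 per group, power is 80.0%. The stated retention gives 40 x 0.80 = 32 to 40 x 0.85 = 34 per arm, with power 82.3% to 84.3% on the same basis.

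**Assumptions.** The documents give no CCQ variance or correlation. Let each reading have variance 1, let rho be the correlation of baseline with follow-up, and let r be the correlation between two baseline readings. Per-participant variances are:
- change from one reading: 2 - 2 rho
- change from the mean of two: 1 + (1 + r)/2 - 2 rho
- adjusted for one reading: 1 - rho^2
- adjusted for the mean of two: 1 - 2 rho^2/(1 + r)

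**Worked case, r = 0.8 and rho = 0.5.**
- Change, one reading: 2 - 1 = 1.000
- Change, mean of two: 1 + 0.9 - 1 = 0.900, a cut of 10%
- Adjusted, one reading: 1 - 0.25 = 0.750, a cut of 25% from the change score with no new reading
- Adjusted, mean of two: 1 - 0.5/1.8 = 0.722, a further cut of 0.722/0.750 = 0.963, or about 4%

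**Gain from the second reading across assumed values.** Power is from the noncentral t at 30 per arm, one-tailed 0.05, with effect 0.65/sqrt(variance ratio). Each column takes its own single-reading analysis as the 80% starting point.

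| r / rho | Change score: variance cut, power | On top of adjustment: variance cut, power |
|---|---|---|
| 0.7 / 0.7 | 25%, 89.0% | 17%, 86.1% |
| 0.5 / 0.5 | 25%, 89.0% | 11%, 84.0% |
| 0.7 / 0.5 | 15%, 85.4% | 6%, 82.1% |
| 0.8 / 0.5 | 10%, 83.6% | 4%, 81.3% |
| 0.9 / 0.5 | 5%, 81.8% | 2%, 80.7% |
| 0.9 / 0.3 | 3.6%, 81.3% | 0.5%, 80.2% |

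The 25% figure arises whenever r = rho. It is a limiting case, because two readings taken days apart would have to agree no better than readings taken weeks or months apart.

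**The two remedies on one scale.** Here d is standardised on the single-reading change SD, so the starting point is 80.0% throughout.

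| r / rho | Second reading alone | Adjustment alone | Both |
|---|---|---|---|
| 0.8 / 0.5 | 83.6% | 89.0% | 90.0% |
| 0.7 / 0.7 | 89.0% | 85.4% | 90.6% |

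**Shared error.** With all correlations equal, two change scores from the same single baseline have covariance 1 - rho and variance 2(1 - rho), so they correlate 0.50. With the mean of two readings, the covariance is (1 - rho)/2 and the variance 1.5(1 - rho), which gives 0.33.

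**The case against.** One baseline reading is a common and valid design. Its noise is equal in expectation in both randomised arms, so there is no bias, and the same remark could be made of most change-from-baseline trials. The Statistical Analysis section already names linear mixed models. A model with baseline as covariate, or with a common baseline mean, removes much of the cost without asking anything of participants. If two readings days apart agree very closely, the extra gain is close to nil.

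The second reading also has limits. Randomisation falls within the screening phase, so a reading on the first stimulation day is taken after it. The 48-hour abstinence requirement is an entry criterion and is not restated for stimulation days, so the two readings may reflect different periods of abstinence.

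Most of this stands, and it makes the point an optional improvement. It does not remove the point: the outcome is worded as change, baseline adjustment is nowhere specified, and a second reading adds some precision even after adjustment. The reading after randomisation is acceptable as a baseline while allocation stays blinded. Section G describes operator-blind software, and before the first session the participant has felt neither condition.

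A reader might infer three stronger things that the documents do not support:
- **The baseline error enters the effect in full whatever the analysis.** It does so only for an unadjusted difference in change.
- **Only 30 per arm will be analysable.** That is the number required; the stated retention gives 32-34.
- **The plan states that the CCQ is given once before treatment.** It does not say so. This is inferred from one listed time point with no repeat.

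**Conclusion.** The point holds as a cheap gain in precision on the main endpoint. At 30 per arm and the plan's d = 0.65, a second reading cuts variance by about 4-25% if change scores are analysed (power from 80% to about 81-89%). On top of baseline adjustment it cuts variance by about 0.5-17% (power from 80% to about 80-86%). These ranges rest on assumed correlations of 0.5-0.9 between baseline readings and 0.3-0.7 between baseline and follow-up, and on d being standardised on the score analysed. Stating the adjustment is often the larger gain: at 0.8/0.5 it removes 25% of change-score variance, against 10% for the second reading alone. It would be wrong to conclude that the design is invalid or that 30 per group is miscalculated.

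**What to change.** 1. In section D, add a CCQ on arrival on the first stimulation day, before motor threshold, cue pictures and TMS.
2. In the synopsis and section F, define baseline CCQ as the mean of that reading and the one from the baseline visit, or the single reading if the other is missing.
3. In Statistical Analysis, state that this mean is the baseline covariate in the linear mixed model already named, with the three later CCQ values as the outcomes.

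The cost is about 10 minutes per participant, or 80 x 10 = 800 minutes (about 13 hours) over the trial, at a visit that already exists, plus a sentence or two of text. The downsides are a slightly longer first stimulation day and a reading taken after randomisation; the protocol should say that it counts as baseline only because allocation is still blinded. Item 3 is worth making even if the second reading is declined, using the one existing value.

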On the basis of these findings, the aim of this study is to test whether rTMS of the left DLPFC could be effective in treating CUD.

C. Study Overview

This is a between-subject double-blind, randomized, sham-controlled study with a 1:1 allocation into two parallel arms: 15 Hz, or sham rTMS stimulation. Participants will be 80

treatment-seeking patients, between the ages of 18-65, who meet diagnostic criteria for CUD (moderate to severe). Criteria for study enrollment are listed below. All participants will be informed about study procedures and will provide written informed consent prior to the experiment, in line with the Helsinki Declaration developed by the World Medical Association.

Recruitment: We aimed to recruit patients from rural and urban areas, in order to take account of possible differences in substance consumption and addiction severity. Therefore, recruitment will take place in two different cities: Rome, a large metropolitan area, and Chieti, a small city in the center of Italy, where the majority of patients will be enrolled from rural surroundings. Participants enrollment will be performed by a multidisciplinary team (physicians, psychologists), who have been trained and have extensive experience in performing the assessments included in the current study.

Inclusion criteria

- 1. Age 18 65;
- 2. Current diagnosis of cocaine use disorder (from moderate to severe), based on the Diagnostic and Statistical Manual of Mental Disorder Fifth Edition (DSM-5);
- 3. Abstinence from cocaine for at least 48 hrs.

Exclusion criteria

- Current DSM-5 diagnosis of substance use disorders other than nicotine Current DSM-V diagnosis of moderate to severe alcohol use disorders
- 2. Current DSM-5 diagnosis of schizophrenia, bipolar disorder, or other psychotic disorder;
- 3. Use in the past 4 weeks of any medication with known proconvulsant action; or current regular use of any psychotropic medications (benzodiazepines, antipsychotic medications, tricyclic antidepressants, anti-epileptics, mood stabilizers);
- 4. Any history of any clinically significant neurological disorder, including organic brain disease, epilepsy, stroke, brain lesions, multiple sclerosis, previous neurosurgery, or personal history of head trauma that resulted in loss of consciousness for > 5 minutes and retrograde amnesia for > 30 minutes;

- 5. Any personal or family history (1st degree relatives) of seizures other than febrile childhood seizures;

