If subjects are unable or unwilling to attend these visits, they will be contacted by phone or email, and an attempt will be made to obtain measures in this manner.

F. Objectives

Primary: The primary goal of the current study is to investigate the effects of repetitive transcranial magnetic stimulation (rTMS) targeting the left DLPFC on cocaine craving. The co-primary goal is to investigate rTMS effect on cocaine consumption.

Secondary: Our secondary goals are to evaluate rTMS effects on: (1) mood; (2) cognitive functions.

Exploratory: Our exploratory goals are evaluating rTMS effects on: (1) BOLD response in DLPFC during tasks known to activate this area; (2) resting state functional connectivity between the DLPFC and nodes of the executive control networks.

Outcomes measures: Our primary outcomes will be: (1) change in craving score as measured by the CCQ from pre- to post treatment [baseline and after rTMS treatment: 2 weeks, 3 months, 6 months]; (2) changes in cocaine consumption as measured by TLFB self-reports and urine drug screen from pre- to post treatment [baseline and after rTMS treatment: 2 weeks, 3 months, 6 months]. Our secondary outcomes are: Changes in the scores on the 90

Symptoms Questionnaire (SCL-90) from pre- to post treatment [baseline and after rTMS treatment: 2 weeks, 3 months, 6 months]; (2) changes in the scores of the Montgomery-Asberg Depression Scale (MADRS) from pre- to post treatment [baseline and after rTMS treatment: 2 weeks, 3 months, 6 months]; (3) changes in the scores on the Hamilton Anxiety Rating Scale (HARS); (4) changes in the scores on the frontal assessment battery (FAB), and on the Flanker task from pre- to post treatment [baseline and after rTMS treatment: 2 weeks, 3 months, 6 months];

(5) changes in the scores of the Iowa Gambling Task from pre- to post treatment [baseline and after rTMS treatment: 2 weeks, 3 months, 6 months];

In addition, in order to investigate DLPFC engagement by TMS, the following exploratory outcomes will be analyzed: (1) DLPFC BOLD signal change in response to cocaine-related stimuli from baseline to each time point [baseline and after rTMS treatment: 2 weeks, 3 months]. (2) Change in resting state functional connectivity, from baseline to each time point (z-score) [baseline and after rTMS treatment: 2 weeks, 3 months].

1. Aims

Primary aim:

To determine the effects of rTMS on cocaine craving and consumption in patients with CUD.

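### Entry requires at least 48 hours of cocaine abstinence, so a co-primary that includes pre-to-post change in negative urines has a baseline shaped by the entry rule, which makes within-arm change hard to interpret and usually costs precision

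*Combined protocol and SAP*

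**What the plan says.** Inclusion criterion 3 (C. Study Overview) asks for "Abstinence from cocaine for at least 48 hrs". It gives no time anchor (screening, randomisation or first session) and no method of verification.

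Section E (Study Design) says of the screening phase: "This phase will include informed consent and randomization, and will conclude with baseline data collection". Baseline therefore comes from people selected under that rule.

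The primary aim (F. Objectives, 1. Aims) lists, for consumption, "Percent of negative urine samples between the active rTMS and sham group, and from pre- to post treatment", at baseline, 2 weeks, 3 months and 6 months. The outcomes text, in the synopsis and again in section F, is broader: "changes in cocaine consumption as measured by TLFB self-reports and urine drug screen from pre- to post treatment".

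The Statistical Analysis section says behavioural and questionnaire measures "will be compared both within and between experimental groups using mixed, repeated-measures ANOVA, and linear mixed models". It names no model for the urine proportion.

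On sampling, the stimulation-day schedule (D. Procedures, rTMS) lists "Tox drug screen" on arrival, before stimulation. No series of pre-treatment urines is scheduled, and nothing says how a percent is formed at baseline. For self-report, section D states: "A lifetime TLFB will be administered at baseline and during each visit".

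**The concern.** A urine test for recent use, taken shortly after a required pause, reflects the entry rule as well as the participant's usual use. A participant who is negative at entry can only stay level or get worse on this measure. Someone negative at entry who then remains abstinent through 2 weeks of treatment and 24 weeks of follow-up scores zero change. Someone negative at entry who returns to use at half the former rate scores as unchanged or worse.

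The within-arm part of the co-primary could therefore show use rising in both arms when active treatment is clearly better than sham. A second issue is precision. If the arms are compared on change, and the baseline percent rests on one test scored 0 or 100, the noise of that test enters the contrast.

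**Working it through.** **1. The plan's own figure.** The power paragraph gives d = 0.65, one-tailed α = 0.05 and about 30 per group. Power is not stated. At 80%, the normal approximation and the noncentral t both give 30 per group. Retention of 80–85% of 40 leaves 40 × 0.80 = 32 to 40 × 0.85 = 34. The figure reproduces. The abstinence rule plays no part in it, and nothing below changes it.

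**2. Ceiling on within-arm change.** Let b be the proportion negative at baseline. The largest possible mean gain is 100 × (1 − b) points. The document does not give b, so the whole range is shown.

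| b (assumed) | Largest gain, points |
|---|---|
| 0.2 | 80 |
| 0.5 | 50 |
| 0.8 | 20 |
| 0.9 | 10 |
| 1.0 | 0 |

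Now assume post-treatment rates of 70% (active) and 40% (sham), with b = 0.8. Active changes by 70 − 80 = −10 points and sham by 40 − 80 = −40. Both arms appear to worsen. The between-arm difference is −10 − (−40) = 30 points, the same as 70 − 40, and it is 30 at every b.

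**3. Precision of a change contrast.** Assumptions, none from the document: post-treatment SD of 35 points, a true difference of 25 points, 30 per arm, two-sided α = 0.05, and one baseline test scored 0 or 100.

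- Baseline SD: s0 = 100 × √(b(1 − b)). This is 40.0 at b = 0.80, 30.0 at 0.90 and 21.8 at 0.95.
- SD of change: √(35² + s0² − 2 × r × 35 × s0), where r is the correlation of baseline with outcome.
- Example, b = 0.80 and r = 0: √(1225 + 1600) = 53.2.
- Power: two-sample noncentral t with 58 degrees of freedom.

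| Analysis | Power |
|---|---|
| Post-treatment values only (SD 35) | 78% |
| Change, b = 0.80, r = 0 | 43% |
| Change, b = 0.80, r = 0.3 | 57% |
| Change, b = 0.80, r = 0.5 | 71% |
| Change, b = 0.50, r = 0 | 34% |
| Change, b = 0.90, r = 0 | 54% |
| Change, b = 0.95, r = 0 | 64% |
| Change, b = 1.00 | 78% |

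**4. Break-even.** Change has the smaller SD when s0² < 2 × r × 35 × s0, that is, when r > s0/70. This gives 40.0/70 = 0.57 at b = 0.80, 30.0/70 = 0.43 at 0.90 and 21.8/70 = 0.31 at 0.95.

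**5. Separate check.** A simulation with single binary outcomes used 30 per arm, 70% against 40% post-treatment, baseline independent of outcome and two-sided α = 0.05. Post-only power was about 66–67% at every b tried. Power on raw change was about 46% at b = 0.2, 38% at 0.5, 47% at 0.8 and 67% at 1.0. The direction agrees with step 3.

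**The case against.** A reader might infer that the co-primary has little room to improve, or cannot show a benefit. The document does not support that. Forty-eight hours of abstinence implies a negative urine only if the detection window is 48 hours or less, and no window, cut-off or baseline rate is given. A participant who is positive at baseline and then abstinent gains 100 points. Room for improvement may be large or nil.

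The main comparison is also intact. The design section states: "This is a between-subject double-blind, randomized, sham-controlled study with a 1:1 allocation into two parallel arms". The entry rule applies to both arms, and the primary aim names the between-arm comparison in the same line as the pre-to-post change. No text prescribes subtracting one entry test. A single baseline sample is itself an inference: the first stimulation-day screen precedes treatment, and section D allows an additional visit before treatment begins.

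The ceiling and the noise also work against each other. Above 50% negative, the more the rule selects negatives, the less noise subtraction adds. The power loss is thus a general weakness of change from a binary baseline, not damage done by the abstinence rule.

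Finally, the outcomes text measures consumption by TLFB as well as urine, and the lifetime TLFB reaches use before the 48 hours.

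All of this stands, and it limits the point to interpretation and precision. It does not rescue the within-arm urine change: the primary aim lists urine alone for consumption, includes the pre-to-post element, and leaves the baseline urine undefined.

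**Conclusion.** The point holds in a limited form. The entry rule tends to shift the baseline urine towards negative by an unknown amount. To the extent that it does, within-arm change is capped and mainly measures return to use, so it is weak evidence of reduced consumption. The randomised contrast is unbiased and the sample-size calculation is unaffected.

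If the arms are compared on change from a single 0/100 test, the usual result is lost precision: under the stated assumptions, 43–71% power against 78% at 80% negative with correlation 0 to 0.5. The loss vanishes at 100% negative. Change gains only above a correlation of about 0.57, 0.43 or 0.31 at 80%, 90% or 95% negative. These figures rest on the assumed SD, difference, baseline rate and single baseline test. The general direction depends less on them, since any b strictly between 0 and 1 adds noise unless the correlation is high enough.

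**What to change.** In the synopsis outcomes, the section F outcomes and the primary aim, make the primary urine contrast the between-arm difference in post-baseline negative urines at the stated 2-week, 3-month and 6-month assessments, without subtracting the entry urine. State which samples count towards each assessment.

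Adjust for cocaine use before the qualifying abstinence, taken from the baseline TLFB; use days in the 28 days before that period would serve. Report within-arm urine change as descriptive only. Leave the entry criterion unchanged.

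The cost is wording and one covariate from data already collected, with no new visits or tests. The plan gives up an inferential pre-to-post statement on urine. If the entry test turned out to correlate with outcome above the break-even values, an unadjusted change analysis would have been somewhat more precise than unadjusted post-treatment values.
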